9.6.2 Exclusion Criteria

All Subjects

1. Subjects who experienced an ARQ-151 treatment-related AE or a serious AE (SAE) that precluded further treatment with ARQ-151 cream in Study ARQ-151-201.
2. Subjects that use any Excluded Medications and Treatments (see [Table 1](#)).
3. Subjects currently taking lithium or antimarial drugs.
4. Planned initiation or changes to concomitant medication that could, in the opinion of the Investigator, affect psoriasis vulgaris (e.g. beta blockers, ACE inhibitors).
5. Current diagnosis of guttate, erythrodermic/exfoliative, palmoplantar, or pustular psoriasis.
6. Subjects with any condition on the treatment area which, in the opinion of the Investigator, could confound safety or efficacy measurements.
7. Known allergies to excipients in ARQ-151 cream
[REDACTED]
8. Subjects who cannot discontinue the use of strong P-450 cytochrome inhibitors e.g., indinavir, nelfinavir, ritonavir, clarithromycin, itraconazole, ketoconazole, nefazodone, saquinavir, suboxone and telithromycin during the study period.

9. Subjects who cannot discontinue the use of strong P-450 cytochrome inducers e.g., efavirenz, nevirapine, glucocorticoids, barbiturates (including phenobarbital), phenytoin, and rifampin during the study period.
10. Subjects who have received oral roflumilast ([Daxas®](#), [Daliresp®](#)) within the past 4 weeks.
11. Known or suspected:
 - severe renal insufficiency or moderate to severe liver impairment (Child-Pugh B or C)
 - hypersensitivity to component(s) of the investigational products
 - history of severe depression, suicidal ideation
12. Females who are pregnant, wishing to become pregnant during the study, or are breast-feeding.
13. Subjects with any serious medical condition or laboratory abnormality that would prevent study participation or place the subject at significant risk, as determined by the Investigator.
14. Subjects with a history of chronic alcohol or drug abuse within 6 months of initiation of study medication.
15. History of and/or concurrent condition of serious hypersensitivity (anaphylactic shock or anaphylactoid reaction) to PDE-4 inhibitors.
16. Current or a history of cancer within 5 years with the exception of fully treated skin basal cell carcinoma, cutaneous squamous cell carcinoma or carcinoma in situ of the cervix.
17. Subjects who are unable to communicate, read or understand the local language, or who display another condition, which in the Investigator's opinion, makes them unsuitable for clinical study participation.

Cohort 1 Only

18. Subjects who experienced an ARQ-151 treatment-related AE or a serious AE (SAE) that precluded further treatment with ARQ-151 cream in Study ARQ-151-201.

Cohort 2 Only

19. Subjects who cannot discontinue medication and treatments prior to the Day 1 visit Excluded Medications and Treatments ([Table 2](#)).

9.6.3 Removal of Subjects from the Study

Subject participation in this trial may be discontinued for any of the following reasons:

1. Occurrence of any medical condition or circumstance that, in the opinion of the Investigator, exposes the subject to substantial risk and/or does not allow the subject to adhere to the requirements of the Protocol.
2. Occurrence of a treatment-emergent adverse event (TEAE) or considerable worsening of an AE that, in the opinion of the investigator in consultation with the Medical Monitor and

Sponsor, represents an unacceptable risk to the subject if he/she continues in the study. The investigator must follow the subject until the AE resolves or satisfactorily stabilizes.

3. Pregnancy.
4. Subject's decision to withdraw.
5. Weight loss of >5% if not dieting or intentionally trying to lose weight and after consultation with the Sponsor, at the Investigator's discretion.
6. C-SSRS indicative of suicidal ideation or a PHQ-8 score ≥ 15 , after consultation with a mental health professional, the Sponsor, and at the Investigator's discretion.
7. Requirement for use of prohibited concomitant medication.
8. Subject's repeated failure to comply with protocol requirements or study related procedures.
9. Termination of the study by the Sponsor, FDA, or other regulatory authorities.

9.7 Study Restrictions

9.7.1 Prohibitions and Concomitant Therapy

Prohibited medications and products are detailed in [Table 1](#) (Excluded Medications and Treatments).

Generally, the addition of new medications, including nonprescription medications, during the course of the study is discouraged. However, it is recognized that this is a 52-week study and subjects may be required to start chronic medications for health benefits. The use of such chronic medications may be authorized by the Investigator. The Investigator must make the decision to authorize the use of any such medication only after consideration of the clinical situation, the potential for masking symptoms of a more significant underlying event, and whether the use of the medication will compromise the outcome or validity of the clinical investigation. Short-term medications, such as antibiotics to treat acute infections, are allowed. If medication is required, the name, strength, frequency, duration of use, and reason for use will be recorded in source documents and transcribed to Case Report Forms. Medications which have already been used chronically by subjects, in particular statins and anti-hypertensives, are allowed for use during the study.

Table 1. Excluded Medications and Treatments

Excluded Medications and Treatments	
Systemic treatment with biological therapies with a possible effect on psoriasis vulgaris	
Systemic treatment with all other therapies with a possible effect on psoriasis vulgaris (eg, oral corticosteroids, retinoids, apremilast, methotrexate, cyclosporine and other systemic immunosuppressants)	
Topical anti-psoriasis medications (e.g., corticosteroids, vitamin D analogs, prescription shampoos) (except for emollients)	
PUVA phototherapy	
UVB	
Investigational drugs (except ARQ-151 cream)	
Note: 
 • Eye drop and nasal corticosteroid preparations are allowed. • Inhaled corticosteroid preparations are allowed if used for a stable condition and at a stable dose for > 28 days before Day 1, and are continued at the same dose throughout the study. • Non-medicated emollients, moisturizers and sunscreens will be allowed as used normally by the subjects. These can be applied to non-treated areas as needed. Study medication should be applied at least 20 minutes before going to bed and no other emollients or moisturizers should be applied to the treated area. • A tar-containing or a dandruff shampoo (zinc pyrithione or selenium sulfide) shampoo is allowed for treatment of the scalp. 	

Table 2. Wash Out Period for Medications and Treatments (Cohort 2)

Excluded Medications and Treatments	Wash Out Period Prior to Day 1
• Systemic treatment with biological therapies with a possible effect on psoriasis vulgaris within the following time periods prior to enrollment:	
Etanercept	4 weeks
Adalimumab, infliximab	8 weeks
All other biologics	12 weeks
• All other therapies with a possible effect on psoriasis vulgaris:	
Oral corticosteroids, retinoids, apremilast, methotrexate, cyclosporine and other systemic immunosuppressants	4 weeks
Topical anti-psoriasis medications (e.g., topical corticosteroids, vitamin D analogs, prescription shampoos) (except for emollients)	2 weeks
PUVA phototherapy	4 weeks
UVB	2 weeks
Systemic retinoids	12 weeks
Investigational drugs	12 weeks (biologics); 5 half-lives (orals); 2 weeks (topical)

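### Sections 9.6.2 and 9.7.1 give sites contradictory instructions on strong P-450 inhibitors and inducers during the study, including three antibiotics named as exclusions

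*Protocol*

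**What the plan says.** Four places in the protocol bear on this.

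- **Section 9.6.2, exclusion 8** (synopsis item 7) excludes subjects who cannot discontinue "strong P-450 cytochrome inhibitors e.g., indinavir, nelfinavir, ritonavir, clarithromycin, itraconazole, ketoconazole, nefazodone, saquinavir, suboxone and telithromycin during the study period".
- **Section 9.6.2, exclusion 9** (synopsis item 8) does the same for "strong P-450 cytochrome inducers e.g., efavirenz, nevirapine, glucocorticoids, barbiturates (including phenobarbital), phenytoin, and rifampin during the study period".
- **Section 9.7.1**, which governs concomitant therapy, opens with "Prohibited medications and products are detailed in" Table 1. It discourages new medication in general but recognises that some subjects will need to start chronic treatment: "The use of such chronic medications may be authorized by the Investigator". It then says: "Short-term medications, such as antibiotics to treat acute infections, are allowed". Medication already in chronic use is also allowed.
- **Section 9.6.3, item 7** gives as one possible reason for removal: "Requirement for use of prohibited concomitant medication". The whole list in 9.6.3 is permissive.

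Table 1 covers biologics and other systemic therapies that may affect psoriasis (oral corticosteroids among the examples), topical anti-psoriasis products, PUVA, UVB and investigational drugs. It has no entry for P-450 inhibitors or inducers.

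**The concern.** Both exclusions refer to the study period, so they express an intention that reaches past Day 1. The section that a site would consult once a subject is enrolled does not carry that intention over, and its sentence on antibiotics points the other way for agents that the exclusions name.

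An acute infection is an ordinary event in a 52-week study. If sites follow different sections, the same prescription may be accepted at one site, and recorded as a deviation or raised as a reason for removal at another. The study is single-arm and its primary endpoints are the occurrence of TEAEs and SAEs. Inconsistent handling therefore affects who stays under observation and under what co-medication, with no concurrent control group against which to judge it. Section 12.5 requires every deviation to be documented and reported, which presupposes that a site can recognise one.

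**Working it through.** No arithmetic applies. The check is a comparison of text, and the protocol states no figure to reproduce.

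**Step 1: named agents against Table 1.**

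| Source | Agents or classes named | Found in Table 1 |
|---|---|---|
| Exclusion 8 (inhibitors) | indinavir, nelfinavir, ritonavir, clarithromycin, itraconazole, ketoconazole, nefazodone, saquinavir, suboxone, telithromycin (10) | 0 of 10 |
| Exclusion 9 (inducers) | efavirenz, nevirapine, glucocorticoids, barbiturates, phenytoin, rifampin (6) | 1 of 6, in part |

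The partial match is glucocorticoids. Table 1 lists oral corticosteroids and topical corticosteroids, and its Note allows eye-drop and nasal preparations, and inhaled ones at a stable dose. Exclusion 9 names the class without a route. In total, 10 + 6 = 16 agents or classes are named, and 16 − 1 = 15 have no counterpart in Table 1.

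**Step 2: named agents against the allowances in 9.7.1.** Three of the named agents are antibiotics: clarithromycin and telithromycin (exclusion 8) and rifampin (exclusion 9). The allowance for short-term antibiotics is limited by duration and indication, but not by agent. The allowance for medication already in chronic use has no P-450 exception either. Authorization of a new chronic medication turns on the clinical situation, possible masking of symptoms, and "whether the use of the medication will compromise the outcome or validity of the clinical investigation". Interaction with study drug is not named.

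**Step 3: one case under each section.** A subject is prescribed a short course of clarithromycin for an acute infection at mid-study.

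- Under exclusion 8, this is an agent the subject was to be able to stay off during the study.
- Under 9.7.1, it is not a Table 1 drug, and it falls within the short-term antibiotic allowance.
- Under 9.6.3 item 7, the answer depends on what counts as prohibited. That item cites no table. Read with 9.7.1 it means Table 1 and the agent is not covered; read with 9.6.2 it arguably is.
- Under 12.5, whether there is a deviation to report depends on which of these readings the site takes.

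The readings lead to opposite instructions, and nothing in the protocol says which section prevails.

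**The case against.** **An exclusion criterion is an entry test.** It asks whether the subject can discontinue, and on that view 9.7.1 alone governs later use and nothing conflicts. This does not dispose of the point. Both criteria are framed over the study period, so confining them to entry leaves that phrase without effect.

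**The protocol does restrict use.** A reader might infer that interacting drugs are permitted freely, or for the full 52 weeks. The text does not support this. The antibiotic sentence covers short-term treatment of acute infections, new medication is discouraged, and new chronic medication needs Investigator authorization with a test of study validity. What is missing is a limit by agent.

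**Removal remains possible.** A reader might infer that no removal decision can arise. That is also too strong. Item 7 does not cite Table 1, the list compels removal for no one, and items 1 (substantial risk, or inability to adhere to the protocol) and 8 (repeated non-compliance) are separate routes. What stands is that it is unclear whether item 7 applies.

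**The data can be traced.** Section 9.7.1 records the name, strength, frequency, duration and reason for each medication; 11.2.8 lists and tabulates them; 11.2.1 lists AE start and stop dates. Events during use of a listed agent can therefore be identified afterwards. This is correct, and no new data item is needed, but it does not settle what sites are told to allow.

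**Harm is not demonstrated.** This is also correct. The readable text gives no reason for exclusions 8 and 9, the sections on dose selection and risk are redacted, and safety analysis is descriptive. No change in TEAE or SAE rates can be claimed.

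**Conclusion.** The contradiction is real. The exclusions treat strong P-450 inhibitors and inducers as agents to be avoided during the study. The on-study list omits 15 of the 16 named agents or classes and covers the other only in part, and 9.7.1 allows short-term antibiotics without excepting the three that the exclusions name. Sites lack one instruction on use, on the applicability of removal reason 7, and on deviation reporting.

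The conflict is in a rule that applies at approximately 30 sites and to up to approximately 300 + 100 = 400 subjects. How many would receive a listed agent is unknown, since the protocol gives no rate of use and any count would be invented. The conclusion assumes only that the words about the study period in exclusions 8 and 9 are meant to have effect after Day 1. It does not assume a particular interaction effect from a topical product. Because this is a rule of conduct, a statistical analysis plan could not resolve it. It should be corrected as a consistency matter relevant to subject safety.

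**What to change.** Reconcile 9.6.2 items 8 and 9 (with synopsis items 7 and 8), 9.7.1 with Table 1 and its Note, and 9.6.3 item 7, so that together they give one consistent instruction on on-study use of these agents. The reconciled text should make three things clear:

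- how the short-term antibiotic allowance applies to the antibiotics that the exclusions name;
- whether such use falls under removal reason 7;
- whether such use is a protocol deviation.

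Which rule is right is a clinical decision for the sponsor, and this review does not propose one.

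The cost is amendment wording, a memo to sites and some added medication queries. No change to data collection is required.

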9.8 Investigational Product and Treatment

9.8.1 Drug Supplies, Packaging and Labeling

ARQ-151 cream 0.3% will be provided in 45 gram squeeze tubes. The tubes will be packaged in kits, each containing 8 tubes of investigational product. The number of kits dispensed to a subject will be based on the BSA involvement of psoriasis. It is anticipated that the maximum number of kits dispensed to a subject will be ten. The kits and tubes will be labeled including a location to record the subject ID on the label.

The Sponsor will supply sufficient quantities of the study drug (ARQ-151 cream 0.3%) to each site to allow for completion of this study.

Records will be made of the receipt and dispensing of the study drugs supplied. At the conclusion of the study, any unused study drugs will be returned to the Sponsor or designee, or destroyed, as per Sponsor instructions.

9.8.2 Treatment Administration

At the Day 1 visit, subjects will be instructed to apply study medication once daily. All subjects should apply medication each evening at least 15 minutes after showering or bathing (if they take an evening shower/bath) and then not wash areas where ARQ-151 cream has been applied until the following morning. Study medication should be applied at least 20 minutes before going to bed.

Subjects should continue to apply study medication to all active psoriasis lesions including any new plaques that develop during the study. A Body Diagram should be used to record existing and new areas of psoriasis involvement that are subject to treatment.

Psoriasis plaques that have completely resolved, in the opinion of the investigator, do not require continued treatment. If psoriasis plaques appear to resolve at some time between study visits, study medication should continue to be applied until the next scheduled visit. At that visit, the Investigator will perform an assessment and determine whether or not to discontinue treatment.

Study medication will be weighed prior to dispensing at all visits where study medication is dispensed. Study medication, both empty and full tubes, must be returned by subjects at each study visit and will be weighed.

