Exclusion Criteria Cohort 2 Only	18. Subjects who cannot discontinue medication and treatments prior to the Day 1 visit according to Excluded Medications and Treatments (Table 2).
Number of Subjects	Up to approximately 300 subjects (Cohort 1) Up to approximately 100 subjects (Cohort 2)
Duration of Participation for Subjects	Approximately 52 weeks
Study Products	ARQ-151 drug product will be supplied as a 0.3% cream in a squeezable tube.
Planned Dose Level	
 Subjects with up to 25% total BSA of psoriatic lesions will receive ARQ-151 cream 0.3% to be applied QD topically to all lesions. Application will be to all areas affected including the face and intertriginous/genital regions (except for the scalp). Subjects may stop treatment to lesions/areas that have cleared and completely resolved. Treatment may resume in these or new areas should psoriatic lesions emerge during the study. If treatment is judged by the Investigator as being ineffective, then the subject may be withdrawn from the study at any time.
Safety Assessments	Safety will be monitored through application site assessments in the clinic using the method of Berger and Bowman, clinical laboratory testing, 12-lead ECGs, PHQ-8, C-SSRS and AEs.
Safety Analysis	
Adverse Events
 
A subject-by-subject treatment-emergent AE (TEAE) data listing, including verbatim term, preferred term, treatment, severity, and relationship to study drug, will be provided.
 
The number of subjects experiencing AEs and number of AEs will be summarized by treatment using frequency counts.
 
Physical Examinations
 
Vital signs will be collected at all study visits. Physical examinations and 12-lead ECGs will be collected periodically throughout the study.
 
Clinical Laboratory Results
 
Routine blood chemistries will be obtained at all study visits. Urine

	
pregnancy tests will be collected periodically throughout the study.
 
Patient Health Questionnaires
 
PHQ-8 and C-SSRS questionnaires will be completed by the subjects at all study visits. Descriptive statistics will be calculated for the PHQ-8. The C-SSRS will be analyzed per the Scoring and Data Analysis Guide from the Columbia Lighthouse Project.

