8.2.2 Secondary Endpoints

The secondary endpoints are related to efficacy and will include:

- Proportion (%) of subjects achieving an Investigator Global Assessment (IGA) of clear or almost clear, as observed at Week 12 and subsequent scheduled visits.
- In subjects who achieve 'clear' scores for IGA, I-IGA (if applicable **and** mPASI (Modified Psoriasis Area Severity Index) and stop treatment to all lesions, time to re-starting study drug (duration of response).
- Proportion (%) of applicable subjects with intertriginous area involvement, 'I-IGA' score of 'clear' or 'almost clear' at week 12 and subsequent visits
- Proportion (%) of subjects achieving a 75% reduction from Baseline of Modified Psoriasis Area Severity Index-75 (mPASI-75) at weeks 12, 24, 36 and 52 as compared to Baseline.

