9 INVESTIGATIONAL PLAN

9.1 Overall Study Design and Plan

This is an open-label, long-term safety study of ARQ-151 cream 0.3% in subjects with chronic plaque psoriasis involving between 0 and 25% BSA. Eligible subjects will enroll into the long-term safety study on the same day as the Week 12 visit for the previous study (ARQ-151-201) for Cohort 1 and on Day 1 for non ARQ-151-201 subjects in Cohort 2. Study medication will be applied by the subjects topically QD for 52 weeks at home.

A total of up to approximately 300 subjects (Cohort 1) and up to approximately 100 non ARQ-151-201 subjects (Cohort 2) will be enrolled at approximately 30 study sites in the United States and Canada. Subjects will be adult (≥ 18 y/o) males or females with chronic plaque psoriasis. Periodic clinic visits will include assessments for clinical safety, application site reactions evaluated in the clinic using the method of Berger and Bowman, disease improvement or progression, and IGA.

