10.5 Unscheduled Visit

Subjects that clear between scheduled visits should return for an unscheduled visit for the investigator to confirm IGA, I-IGA (if applicable) and mPASI are clear and subject may stop application of study drug. Unscheduled visits may be necessary for the purpose of measuring time to restarting study drug for those subjects that stopped application of study medication due to resolution of psoriasis plaques. Subjects will call the site when psoriasis returns prior to restarting application of study drug. Unscheduled visits also may be necessary to repeat testing following abnormal laboratory results, for follow-up of AEs, or for any other reason, as warranted in the judgement of the Investigator.

The following information will be collected for all subjects:

- Concomitant medications/procedures
- AEs

The following information will be collected for those subjects that had stopped study medication but are experiencing a reoccurrence of psoriasis plaques:

- Time between stopping study medication and restarting application
- Investigator's Global Assessment (IGA) of psoriasis severity
- Body Surface Area (BSA) of psoriasis involvement (not palms, soles, or scalp)

An updated Body Diagram of psoriasis involvement should be provided to the subject.

The rules for how to tally IGA or other proportions of categorical responses will be described in the Statistical Analysis Plan.

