10.8 Treatment Stopping Rules

For subjects that clear (i.e. have an IGA score of 0 (Clear), an I-IGA (if applicable) of 0 (Clear) **and** an mPASI of 0) treatment may be stopped. The subject will be instructed to document in their diary when they resume treatment with study drug if psoriasis returns. If the subject clears between study visits they should be scheduled for an unscheduled visit for the Investigator to confirm the subject has cleared.

Subjects will call the site when psoriasis returns prior to restarting application of study drug.

If a subject has non-cutaneous adverse events of concern, clinically significant laboratory values or any condition that the investigator determines could possibly be related to the study drug, the Investigator should immediately contact the Medical Monitor to discuss if the subject should be discontinued from the study.

Treatment for any individual subject will be discontinued if the subject experiences:

- A serious adverse event (SAE) or a clinically significant non-serious AE which in the opinion of the Principal Investigator or Medical Monitor warrants discontinuation from the study for that subject's well-being.
- A severe (Grade 3) laboratory abnormality (confirmed by repeat sample and considered related to study drug).
 - See [Appendix 2](#) for details.

Dosing of study drug for an individual subject may be suspended for safety concerns other than those described above, at the discretion of the investigator if he/she feels the subject's safety may be threatened.

A subject with a PHQ-8 score of '15' or above should be referred promptly to a mental health care professional and consideration be given to discontinuation from study drug.

A subject that is experiencing suicidal ideation and behavior should be referred immediately to a qualified mental health care provider and consideration given to discontinuation from study drug.

As noted above, study treatment must be discontinued immediately in the event of a female subject's pregnancy.

Treatment should be interrupted:

- If a subject develops an application site reaction with the clinical appearance of an 'irritation reaction', and with a severity of a Dermal Response Score of 5 (erythema, edema and papules) or greater on the scale of Berger and Bowman. Treatment can be interrupted for up to one week and may then be resumed if the reaction has, in the opinion of the Investigator, adequately resolved.

Treatment should be discontinued:

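### When all of a subject's plaques resolve between visits, Section 9.8.2 keeps treatment going to the next scheduled visit, while Sections 10.5 and 10.8 call an unscheduled visit at which it may stop

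*Protocol*

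**What the plan says.** Section 9.8.2 (Treatment Administration) first says that plaques the investigator judges fully resolved need no further treatment. For resolution between visits it then says: "If psoriasis plaques appear to resolve at some time between study visits, study medication should continue to be applied until the next scheduled visit". It continues: "At that visit, the Investigator will perform an assessment and determine whether or not to discontinue treatment".

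Section 10.5 (Unscheduled Visit) says: "Subjects that clear between scheduled visits should return for an unscheduled visit for the investigator to confirm IGA, I-IGA (if applicable) and mPASI are clear". Once that is confirmed, it lets the subject stop applying drug. Section 10.8 (Treatment Stopping Rules) permits stopping when IGA, I-IGA (if applicable) and mPASI are all zero, and adds: "If the subject clears between study visits they should be scheduled for an unscheduled visit for the Investigator to confirm the subject has cleared".

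The synopsis, under Planned Dose Level, says: "Subjects may stop treatment to lesions/areas that have cleared and completely resolved". It names neither a visit nor an assessor.

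The endpoint concerned is in Section 8.2.2. It covers subjects who reach clear scores "and stop treatment to all lesions, time to re-starting study drug (duration of response"). Section 11.3 analyses treatment-free days to first retreatment by Kaplan–Meier. For former vehicle subjects it counts them from the end of initial treatment in this study.

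**The concern.** Take a subject whose plaques have all gone some weeks before the next clinic visit. A site working from Section 9.8.2 keeps the subject on drug and leaves the decision to that visit. A site working from Section 10.5 or 10.8 calls the subject in and may let treatment stop. Stopping is permitted there, not required, so the conflict is over whether the extra visit is held and whether an earlier stop is allowed.

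Subjects who clear and stop treatment to all lesions are the population for duration of response. If the approximately 30 sites follow different sections, comparable subjects would have different permitted stop dates, different exposure before the interval starts and different follow-up left in which relapse can be seen. There is also a compliance side. Section 12.5 bars deviations outside emergencies, and a site that acts on one instruction can appear to depart from the other.

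**Working it through.** **The texts side by side, full clearance between visits**

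| Question | Section 9.8.2 | Sections 10.5 and 10.8 |
|---|---|---|
| Which visit assesses the subject? | Next scheduled visit | Unscheduled visit |
| Treatment until then? | Continue | Not stated; may stop once clearance is confirmed |
| Earliest permitted stop | Next scheduled clinic visit | Date of the unscheduled visit |

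1. *Could the next scheduled visit be the unscheduled one?* Section 10.5 sets the two terms against each other in one sentence. Section 10.1 lists the scheduled visits as Day 1 and Visits 1–5, which Section 5 places at Weeks 4, 12, 24, 36 and 52. The calls at Weeks 18, 30 and 44 only review adverse events and concomitant medication (Section 10.1.9).
2. *Is Section 9.8.2 limited to partial resolution?* It does not say so. When only some plaques resolve, the sections can be read together. When all resolve, both rules apply.
3. *Is precedence stated?* No, and the synopsis does not settle the matter.
4. *Who is unaffected?* Subjects found clear at a scheduled clinic visit, and those already clear on Day 1. Section 9.1 allows the latter, describing disease "involving between 0 and 25% BSA".

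**Size of the difference**

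Inputs from Sections 5 and 9.2: clinic visits at Day 1 and Weeks 4, 12, 24, 36 and 52 (taken as days 0, 28, 84, 168, 252 and 364). Windows are ±3 days at Week 4, ±5 at Week 12 and ±7 at Weeks 24, 36 and 52.

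- Nominal gap = later visit day − earlier visit day.
- Gap with windows = nominal gap + window of the earlier visit + window of the later visit (earlier visit held early, later one late; Day 1 has no window).
- Follow-up left after a stop at a scheduled visit = 364 − visit day. Its maximum with windows = 371 − (visit day − window), with the Week 52 visit on day 364 + 7 = 371.

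| Clearance between | Nominal gap (days) | Gap with windows (days) | Earliest stop under 9.8.2 | Follow-up left, nominal (days) | Follow-up left, maximum (days) |
|---|---|---|---|---|---|
| Day 1 and Week 4 | 28 | 28 + 3 = 31 | Week 4 | 364 − 28 = 336 | 371 − 25 = 346 |
| Weeks 4 and 12 | 84 − 28 = 56 | 56 + 3 + 5 = 64 | Week 12 | 364 − 84 = 280 | 371 − 79 = 292 |
| Weeks 12 and 24 | 168 − 84 = 84 | 84 + 5 + 7 = 96 | Week 24 | 364 − 168 = 196 | 371 − 161 = 210 |
| Weeks 24 and 36 | 252 − 168 = 84 | 84 + 7 + 7 = 98 | Week 36 | 364 − 252 = 112 | 371 − 245 = 126 |
| Weeks 36 and 52 | 364 − 252 = 112 | 112 + 7 + 7 = 126 | Week 52 | 0 | 0 |

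The gap columns are upper bounds on the difference in permitted stop date. They are reached only if clearance follows directly on the earlier visit, and they shrink by the time it takes to hold the unscheduled visit. In the last row, a subject following Section 9.8.2 adds no treatment-free time, against nominally up to 112 days (126 with windows) under Sections 10.5 and 10.8.

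**The case against.** The best counter-argument uses the opening of the same paragraph in Section 9.8.2, where plaques resolved in the investigator's judgement need no further treatment. On that view, the instruction to continue only stops subjects from quitting on their own impression. The unscheduled visit then supplies the investigator's judgement earlier, and Section 9.8.2 itself is satisfied. One can add that Section 9.8.2 speaks of plaques while Sections 10.5 and 10.8 speak of subjects, and that a specific stopping rule normally overrides a general application instruction.

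This is a sensible way to reconcile the sections, but it is not written down. The sentences that follow the opening place the investigator's decision, for resolution between visits, at the next scheduled visit. The distinction between plaque and subject does not help when every plaque has resolved.

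The objection to weight largely stands. The endpoint is secondary and descriptive, and Section 11.3 says the study is not meant to assess efficacy. The interval runs from actual stop to actual restart. The diary records each dose, and the unscheduled-visit record for a recurrence includes "Time between stopping study medication and restarting application". Subjects who discontinue without relapse are censored, so shorter follow-up mainly costs information. The largest figures need clearance soon after Week 36 and a prompt unscheduled visit. Recording the dates does not, however, make the permitted stop date uniform.

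**Conclusion.** The contradiction holds for subjects whose plaques all resolve between clinic visits, and only for them. The permitted stop date can differ by at most 28 to 112 days nominally, or 31 to 126 days with windows, depending on the interval. After Week 36 the choice of section decides whether a subject who clears between visits and completes the study can contribute any treatment-free follow-up.

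These bounds rest on the visit schedule, on subjects completing the study, and on sites following one section or the other as written. The protocol gives no distribution of clearing times, so no average effect can be stated, and the direction of any bias cannot be derived. The primary safety endpoints (Section 8.2.1) do not depend on this. It should be corrected, but it does not threaten the study's main purpose.

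**What to change.** Reconcile Sections 9.8.2, 10.5 and 10.8, and the synopsis wording under Planned Dose Level, so that one rule applies to full clearance between visits. The rule should say which visit assesses the subject and when application may stop. State separately what applies when only some plaques resolve, and cross-refer between the sections. Which rule to keep is a clinical decision for the sponsor, and no view is offered here. The cost is protocol wording and a memo to sites, whichever rule is kept.
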